iTIND Device will be implanted for 5-7 days. Sham will be a routine Foley catheter placement and removal procedure conducted at the implantation visit and at the device retrieval visit.

SAFETY VARIABLES:

- Incidence (% of patients) and frequency (no. of events) of device related adverse events
- Incidence (% of patients) and frequency (no. of events) of any adverse events
- Safety laboratory measurements
- Vital signs and physical examinations

EFFICACY VARIABLES:

Primary Endpoint:

The primary efficacy endpoints for this study are:

- Change from baseline to month 3 in the IPSS/ AUA-SI Score. Analysis will compare the differences between the two study groups.
- Change from baseline to month 12 in the IPSS/ AUA-SI Score. Analysis will assess the within iTIND group change.

Secondary Endpoints:

Analysis will compare the differences between groups in:

- Change from baseline to month 3 in IIEF (International Index of Erectile Function),
- Change from baseline to month 3 in SHIM (Sexual Health Inventory for Men)
- Change from baseline to month 3 in Qmax (maximum urinary flow rate)
- Change from baseline to month 3 in PVR (post-void residual urine volume),

STATISTICAL METHODOLOGY:

A total of 170 subjects randomized to treatment with either iTIND arm or to the control arm using a respective randomization scheme of 2:1 are expected to be recruited into this trial. Since it is anticipated that some of the participating sites will recruit an insufficient number of subjects to allow estimation of within sites effect size or treatment by site interaction study centers will be pooled into Country/Geographical Region (CGR).

Randomization:

Subjects will be randomized using a 2:1 assignment ratio to either iTIND group or to the control group, respectively. Randomization will employ permuted blocks stratified by center.

Overall Significance Level:

The overall significance level for this study will be 5% using two-tailed tests. To preserve the overall type-I error of the study the following will take place:

- The study identifies two primary endpoints and four secondary end-points ordered in a hierarchy.
- Meeting both primary endpoints at type-I error of 5% each, is sufficient to determine study success in demonstrating the effectiveness and effect durability of iTIND treatment.
- Secondary endpoints will be tested only if both primary endpoints are met.

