- Analysis suggested that for the 12-month change analysis of the iTIND arm a total of 100 subjects will provide a power of 97.8% for this endpoint.

Principal Analysis of the Two Primary Endpoints

- Subjects prescribed with alpha blockers or with 5-ARIs following initiation of study treatment and up to the period that ends at 12-month follow-up visit will be considered, for the purpose of statistical analysis, as treatment failures starting from the date in which these medications were administered. To account for this potential source of bias in the analysis, all IPSS/AUA-SI measurements of an individual subject, starting from the date of initiation of alpha blockers or 5-ARIs administration will be imputed to be their baseline values.
- The principle analysis of the two primary endpoints will be performed for the ITT analysis

set. The statistical model to be used for inference of the two primary endpoints will be a repeated measures model (SAS® MIXED procedure with REPEATED sub-command). The model will include the following fixed effects: categorical month in trial by treatment interaction and baseline IPSS/AUA-SI measurement as one degree of freedom covariate. The unstructured covariance matrix for repeated observations within subjects will be used. In case that the model will not converge, the Maximum-Likelihood (ML) estimation method will be used instead of the default Restricted ML (REML). If the model still does not converge then a simpler covariance structures with less parameters will be used, according to the following order: Heterogeneous Autoregressive(1) (ARH(1)), Heterogeneous Compound Symmetry (CSH), Autoregressive(1) (AR(1)), and Compound Symmetry (CS).

- The Least Square Means (LSM) at Month 3 visit of the change from baseline will be compared between the iTIND arm and the control group and will be used for inference regarding the first primary endpoint.
- The Least Square Means (LSM) at Month 12 visit of the change from baseline within the iTIND arm will be used for inference regarding the second primary endpoint. In the case that the Lower CI of the Least Squares Means SAS table will be higher than 1 IPSS/ AUA-SI score point then a positive inference will be made regarding the second primary endpoint.
- Study will be considered positive if both primary endpoints are met.
- To assess the robustness of results and conclusions and the potential impact of missing values a comprehensive set of sensitivity analysis will be performed.

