Statistical Analysis Plan (SAP)

The study will be conducted when the Sponsor and the Biostatistician assigned to the study are fully blinded to treatment assignment. A more detailed SAP will be developed by the statistician prior to revealing of the study blind.

I. STATISTICAL METHODOLOGY

A total of 170 subjects randomized to treatment with either iTIND arm or to the control arm using a respective randomization scheme of 2:1 are expected to be recruited into this trial. Since it is anticipated that some of the participating sites will recruit an insufficient number of subjects to allow estimation of within sites effect size or treatment by site interaction study centers will be pooled into Country/Geographical Region (CGR).

A. RANDOMIZATION PROCEDURE

Subjects will be randomized using a 2:1 assignment ratio to either iTIND group or to the control group, respectively. Randomization will employ permuted blocks stratified by center.

B. SAMPLE SIZE RATIONALE

Study power was estimated for both primary endpoints to ensure that study is adequately powered to meet both endpoints.

The first primary endpoint for this study is the change from baseline to month 3 in the IPSS/AUA-SI score and analysis is planned to compare the changes of both study arms. The power of the trial for this endpoint was estimated based the following assumptions for that primary endpoint:

- The expected STD of the 3-month change from baseline for the 2 study arm is 7.35 IPSS/AUA-SI points.
- The expected effect size (difference between the changes in the iTIND arm and the control arm) is 4 IPSS/ AUA-SI points.
- A two-sample t-test employing a 5% two-tailed testing was used to estimate study power.
- Analysis suggested that for an expected effect size of 4 IPSS/ AUA-SI points, STD of change of 7.35 IPSS/ AUA-SI points, using a 5% two-tailed testing, a total of 170 subjects randomized to either iTIND group or the control using a respective randomization scheme of 2:1 will provide a power of 87.7% for this endpoint.

The second primary endpoint for this study is the change from baseline to month 12 in the IPSS/AUA-SI score and analysis will assess the within iTIND group change. The power of the trial for this endpoint was estimated based the following assumptions for that primary end-point:

- The expected mean 12-month change and STD of the 12-month change from baseline for the iTIND arm are 4.0 and 7.35 IPSS/ AUA-SI points, respectively.

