- 1. Change from baseline to month 3 in IIEF (International Index of Erectile Function),
- 2. Change from baseline to month 3 in SHIM (Sexual Health Inventory for Men)
- 3. Change from baseline to month 3 in Qmax (maximum urinary flow rate)
- 4. Change from baseline to month 3 in PVR (post-void residual urine volume),

E. ANALYSIS SETS

a. Intent-to-Treat (ITT) Analysis Set

The intent-to-treat (ITT) population will include all randomized patients according to treatment subjects were randomized to regardless of treatment they actually received.

b. Safety (ST) Analysis Set

The safety population will include all randomized patients who initiated study treatment procedures according to treatment actually administered.

c. 3-Months Completer Analysis Set (CO3M)

The 3-Month completer analysis set (CO_{3M}) will consist of all subjects who complete the 3 months comparative phase of the study.

Note: Subjects who are excluded intra-operatively due to abnormal findings on cystoscopy will not be included in the analysis populations outlined above. Any such exclusions will be reported, including demographics, baseline characteristics and reasons for exclusion.

F. DEMOGRAPHIC BASELINE CHARACTERISTICS ANALYSIS

Demographic and baseline data will be performed for the ITT analysis set. Subject demographic and baseline characteristics, including BPH prognostic factors will be examined to assess the comparability of the treatment groups. Medical history, Prior medications, will be summarized using descriptive statistics. For continuous variables, descriptive statistics (number [n], mean, standard deviation, standard error, median, minimum, and maximum) will be provided. For

categorical variables, subject counts and percentages will be provided. Categories for missing data will be presented if necessary.

G. PLANNED METHOD OF ANALYSIS

All formal pre-defined significance testing will be performed for the ITT Analysis Set.

- a. Principal Analysis of the Two Primary Endpoints

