- Subjects prescribed with alpha blockers or with 5-ARIs following initiation of study treatment and up to the period that ends at 12-month follow-up visit will be considered, for the purpose of statistical analysis, as treatment failures starting from the date in which these medications were administered. To account for this potential source of bias in the analysis, all IPSS/AUA-SI measurements of an individual subject, starting from the date of initiation of alpha blockers or 5-ARIs administration will be imputed to be their baseline values.
- The statistical model to be used for inference of the two primary endpoints will be a repeated measures model (SAS® MIXED procedure with REPEATED sub-command). The model will include the following fixed effects: categorical month in trial by treatment interaction and baseline IPSS/AUA-SI measurement as one degree of freedom covariate. The unstructured covariance matrix for repeated observations within subjects will be used. In case that the model will not converge, the Maximum-Likelihood (ML) estimation method will be used instead of the default Restricted ML (REML). If the model still does not converge then a simpler covariance structures with less parameters will be used, according to the following order: Heterogeneous Autoregressive(1) (ARH(1)), Heterogeneous Compound Symmetry (CSH), Autoregressive(1) (AR(1)), and Compound Symmetry (CS).
- The Least Square Means (LSM) at Month 3 visit of the change from baseline will be compared between the iTIND arm and the control group and will be used for inference regarding the first primary endpoint.
- The Least Square Means (LSM) at Month 12 visit of the change from baseline within the iTIND arm will be used for inference regarding the second primary endpoint. In the case that the Lower CI of the Least Squares Means SAS table will be higher than 1 IPSS/ AUA-SI score point then a positive inference will be made regarding the second primary endpoint.
- Study will be considered positive if both primary endpoints are met.
 - b. Sensitivity Analysis of the Two Primary Endpoints
 - i. Types Of Missing Values

Before revealing of the blind, missing observations will be classified according to the following three types of missing values which are defined according to the relation of the missingness mechanism to observed and unobserved data:

- Missing Completely At Random (MCAR): If the missing value reason deemed unrelated to the observed or to the unobserved IPSS/AUA-SI score

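### Low priority: the month-3 models omit both center, the stratification factor, and its pooled form CGR, so the tests are valid but slightly conservative if center or region is prognostic

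*Combined protocol and SAP*

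**What the plan says.** The Synopsis (Randomization) and SAP section A describe the allocation in the same words: "Randomization will employ permuted blocks stratified by center", in a 2:1 ratio. The SAP's Statistical Methodology paragraph expects some sites to recruit an "insufficient number of subjects to allow estimation of within sites effect size or treatment by site interaction", and for that reason pools centers into CGRs.

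The model for both primary endpoints (Synopsis, Principal Analysis; SAP G.a) contains "fixed effects: categorical month in trial by treatment interaction and baseline IPSS/AUA-SI measurement as one degree of freedom covariate", with an unstructured covariance matrix. The model for the four month-3 secondaries (SAP G.c) is the same, with each parameter's own baseline. Neither contains center or CGR, and after its introduction CGR is not mentioned again in legible text. The responder paragraph (SAP G.b.v) is damaged in the text available, so its full list of effects cannot be read.

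Two further statements matter. The introduction to the SAP says: "A more detailed SAP will be developed by the statistician prior to revealing of the study blind". The note to SAP section E says: "Subjects who are excluded intra-operatively due to abnormal findings on cystoscopy will not be included in the analysis populations outlined above".

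**The concern.** Stratifying by center balances the arms within centers, so most center-to-center variation drops out of the treatment difference. A model without center or region still counts that variation as residual noise. The reported standard error is then larger than the true one: the test rejects less often than 5% under the null, and some available power goes unused. This affects the month-3 primary comparison and the four gated secondaries. It does not affect the month-12 endpoint in the same way, because that endpoint is a within-iTIND mean with no treatment contrast.

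There is also a gap in the plan. Pooling into CGR is announced because site-level effects and interactions could not be estimated, but no regional consistency analysis is legibly specified.

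**Working it through.** **Inputs from SAP section B.** SD of change 7.35, difference 4, two-sided 5%, 2:1 allocation, 170 randomized, stated power 87.7%; 100 iTIND subjects for month 12, expected mean 4, bound 1.

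**Assumed, because the documents do not give them.** The share of outcome variance between centers (5, 10, 15%), the number and size of centers, the number of CGRs, and the block size. The SD of 7.35 is taken as the SD remaining after baseline.

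**1. The plan's own figure.** SE = 7.35 × √(1/n₁ + 1/n₂).
- 100 vs 50: SE = 1.273, 4/1.273 = 3.142, t-test power 87.7%. This matches the stated figure.
- 113 vs 57 (all 170): SE = 1.194, 4/1.194 = 3.350, power 91.5%.

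The plan states: "A two-sample t-test employing a 5% two-tailed testing was used to estimate study power". That calculation uses the total SD and takes no credit for center or region, so omitting them does not reduce 87.7%.

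**2. Limit with complete blocks.** If the arms are exactly balanced within centers, the model SE exceeds the true SE by 1/√(1 − share), and actual type I error = 2 × [1 − Φ(1.96/√(1 − share))].

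| Share | SE inflation | Effective critical value | Type I error |
|---|---|---|---|
| 5% | 1.026 | 2.011 | 4.4% |
| 10% | 1.054 | 2.066 | 3.9% |
| 15% | 1.085 | 2.126 | 3.4% |

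**3. Incomplete blocks.** Single-visit simulation: 150 analysed, 4 CGRs, blocks of 6 within center, share split equally between region and center within region. Type I error is from 60,000 runs (error about 0.08 point); the power change from adding CGR is from 20,000 runs (paired error about 0.1 point).

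| Layout | Share | Type I without CGR | Type I with CGR | Power change, CGR carries half | Power change, CGR carries all |
|---|---|---|---|---|---|
| 16 unequal centers (30 down to 1) | 5% | 4.48% | 4.72% | +0.4 | +0.7 |
| | 10% | 4.13% | 4.59% | +0.9 | +1.4 |
| | 15% | 3.82% | 4.53% | +1.5 | +2.3 |
| 30 centers of 5 | 5% | 4.57% | 4.74% | +0.4 | +0.6 |
| | 10% | 4.24% | 4.57% | +0.7 | +1.4 |
| | 15% | 3.95% | 4.48% | +1.2 | +2.1 |

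At share 0, adding CGR costs 0.1 point in both layouts.

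**4. All 170 analysed.** The complete-block closed form at 113 vs 57 gives gains of 0.4 to 1.0 point if CGR carries half the share and 0.7 to 1.9 if it carries all.

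**5. Repeated measures form.** Simulation with 3 assumed visits, residual correlation 0.6, unstructured covariance, complete data and the 16-center layout (8,000 runs, paired error 0.1 to 0.2 point). Month-3 power change at shares 5, 10 and 15%:
- Region effect the same at all visits: additive CGR +0.5, +1.0, +1.5; CGR-by-month +0.2, +0.9, +1.4.
- Region effect differing by visit: additive CGR +0.1, +0.4, +0.7; CGR-by-month +0.4, +1.0, +1.8.
- Share 0: CGR-by-month −0.1.

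An additive term therefore misses much of a visit-specific region effect.

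**6. Side effect on month 12.** 100 iTIND subjects in assumed region shares 40/30/20/10; power for the lower confidence limit to exceed 1 when the mean is 4.
- Observed region weights: SE = 7.35/√100 = 0.735, power 98.1% (the plan states 97.8%).
- Equal weights, additive CGR, 50 controls helping to estimate region effects: SE 0.806, power 95.8%.
- Equal weights, CGR-by-month, iTIND data only: SE = 7.35 × ¼ × √(1/40 + 1/30 + 1/20 + 1/10) = 0.839, power 94.3%.

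**The case against.** The strongest reply is that nothing here is an error. The model is pre-specified and valid, and the stated power does not depend on center. The pooling sentence speaks of effects and interactions across sites; it does not promise CGR as a covariate. The damaged responder paragraph may contain CGR, and the later SAP may define its use. All of this is true, which is why the point is an omission of low priority and not a contradiction.

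The size can also be argued down. The gains are smaller with all 170 analysed (step 4). If baseline explained 20% of the variance (an assumption), the complete-block closed form at 113 vs 57 gives only about 0.2 to 0.5 point (CGR carrying half) or 0.4 to 0.9 (all), from power of about 97%. Nor do the documents prove that blocks will be incomplete; small sites and intra-operative exclusions make it likely. These arguments trim a gain that is already slight.

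The remedy has a risk of its own: under equal region weights, month-12 power could fall by more than month-3 power rises. That stands, and the change must guard against it.

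**Conclusion.** The point holds, as a low-priority improvement in efficiency. The month-3 models leave out both the stratification factor and its pooled form, and no legible analysis uses CGR. The omission cannot inflate type I error.

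If center or region explains 5 to 15% of the variance, type I error is at lowest 3.4 to 4.4%, and 3.8 to 4.6% in the two incomplete-block layouts; other layouts can be nearer 5%. The unused month-3 power with 150 analysed is 0.4 to 1.5 points if CGR carries half the share and 0.6 to 2.3 if it carries all. If neither center nor region is prognostic, nothing is lost by the present model. At a share of 20% the complete-block limit is 2.8%, which would be more than slight, but nothing in the documents points to a share of that size.

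The gain for the four secondaries cannot be given, because the documents state no SD or effect size for them. All sizes rest on the assumed variance share, center layout, number of CGRs and block size.

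**What to change.** In the detailed SAP, before unblinding:

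1. Fix the list of CGRs and which centers belong to each.
2. Add CGR and CGR-by-month as fixed effects in the repeated measures models for the month-3 primary endpoint and the four secondaries.
3. Add a supportive treatment-by-CGR analysis at month 3, outside the testing hierarchy.
4. For the month-12 iTIND least squares mean, either keep the stated model without CGR or specify observed-proportion region weights, so that its meaning and precision do not change.

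The cost is SAP wording, a few degrees of freedom, and about 0.1 to 0.2 point of month-3 power if region is not prognostic. Keeping the stated model for month 12 means the two primary endpoints no longer share one model; the alternative is a written weighting rule. CGR recovers only the between-region part of center variation, so some conservatism remains: type I error of about 4.7, 4.6 and 4.5% in the 16-center layout.

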- Endpoint will be met if the lower bound of the two-sided 95% confidence interval for that 12-month mean change from baseline calculated for the iTIND arm will be higher than 1

IPSS/ AUA-SI point reflecting a 25% boundary as compared to the expected mean effect size (4.0 IPSS/AUA-SI points).

- A two-sided 95% confidence interval for the 12-month change from baseline within the iTIND arm was used to estimate study power.
- Analysis suggested that for the 12-month change analysis of the iTIND arm a total of 100 subjects will provide a power of 97.8% for this endpoint.

C. OVERALL SIGNIFICANCE LEVEL

The overall significance level for this study will be 5% using two-tailed tests. To preserve the overall type-I error of the study the following will take place:

- The study identifies two primary endpoints and four secondary end-points ordered in a hierarchy.
- Meeting both primary endpoints at type-I error of 5% each, is sufficient to determine study success in demonstrating the effectiveness and effect durability of iTIND treatment.
- Secondary endpoints will be tested only if both primary endpoints are met.
- Type-I error control for multiple endpoints testing will utilize the gate keeping approach performed according to the following hierarchy order:
 - 1. Change from baseline to month 3 in IIEF (International Index of Erectile Function)
 - 2. Change from baseline to month 3 in SHIM (Sexual Health Inventory for Men)
 - 3. Change from baseline to month 3 in Qmax (maximum urinary flow rate)
 - 4. Change from baseline to month 3 in PVR (post-void residual urine volume)

D. EFFICACY ENDPOINTS AND ANALYSES

The study identifies two primary endpoints and four secondary end-points ordered in a hierarchy for significance testing as provided below.

a. Primary Endpoints

The two primary efficacy endpoints for this study which are given in the hierarchy order of significance testing for are:

- 1. Change from baseline to month 3 in the IPSS/ AUA-SI Score. Analysis will compare the differences between the two study groups.
- 2. Change from baseline to month 12 in the IPSS/ AUA-SI Score. Analysis will assess the within iTIND group change.

b. Secondary Endpoints

Secondary endpoints will be tested only if both primary endpoints are met. Analysis will compare the differences between groups at month 3 and significance testing will be performed, utilize the gate keeping approach, according to the hierarchy order outlined below:

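### If the covariance fallback ends in AR(1) or CS and no empirical standard error is specified, the month-12 confidence limit that decides the second primary can be mis-sized when variances differ between visits

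*Combined protocol and SAP*

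**What the plan says.** The cascade appears in the Synopsis (Principal Analysis of the Two Primary Endpoints), in SAP section I.G.a for both primaries, and in SAP section I.G.c for the secondaries. The model is SAS MIXED with a REPEATED statement, month-by-treatment effects, a baseline covariate and an unstructured covariance. If it does not converge, ML replaces REML. After that: "If the model still does not converge then a simpler covariance structures with less parameters will be used". The order given is ARH(1), CSH, AR(1), CS.

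None of the three places names a standard-error estimator or a degrees-of-freedom method. They also do not say whether REML is restored for the simpler structures.

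The second primary is read from the least-squares-means table. It is met if the lower limit of the two-sided 95% interval for the 12-month mean change "calculated for the iTIND arm will be higher than 1" point (SAP I.B). SAP I.C sets the error rate: "The overall significance level for this study will be 5% using two-tailed tests", with 5% for each primary. The opening of the SAP promises a more detailed SAP before unblinding.

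**The concern.** ARH(1) and CSH estimate a separate variance for each visit. AR(1) and CS estimate one common variance, so the model-based standard error at any visit reflects the SD averaged over visits. The second primary rests on one limit, at one visit, in one arm. If the month-12 SD is above the average, that interval is too narrow and the chance of wrongly declaring durability exceeds 2.5%. If it is below the average, the interval is too wide and power is lost.

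Equal variance over visits is not assured. SAP I.G.a sets scores back to baseline from the date alpha blockers or 5-ARIs are started, so the share of zero changes may grow over follow-up. That can make the spread depend on the visit, in a direction that cannot be known beforehand. A fallback triggered by a convergence failure should not also change the error rate.

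**Working it through.** **Inputs from the plan.** Two-sided 5% (SAP I.C). "Subjects will be randomized using a 2:1 assignment ratio" (SAP I.A), so 170 subjects split about 113:57. For month 3, a difference of 4 points, and "The expected STD of the 3-month change from baseline for the 2 study arm is 7.35 IPSS/AUA-SI points". For month 12, "The expected mean 12-month change and STD of the 12-month change from baseline for the iTIND arm are 4.0 and 7.35 IPSS/ AUA-SI points", with a boundary of 1 point and 100 iTIND subjects (SAP I.B).

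**Inputs assumed.** Four post-baseline efficacy visits, with month 3 second and month 12 last (the plan gives 7 visits in all and does not say which record IPSS); all visit SDs other than 7.35; correlations of 0.6 to 0.7; the dropout model.

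**Step 1: the plan's own figures.**
- First primary, two-sample noncentral t: 113:57 gives 91.5%; 100:50 gives 87.7%, the stated figure. The stated power therefore corresponds to 150 analysed subjects, which fits the 100 iTIND subjects used for month 12.
- Second primary, one-sample t with n = 100 and distance 4.0 − 1 = 3: 98.1%, against 97.8% stated.
- The plan gives no figure for the fallback itself.

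**Step 2: AR(1) or CS, complete data.** For CS, model-based SE divided by true SE at a visit = (root mean square of the visit SDs) / (SD at that visit). AR(1) gives nearly the same ratio in the rising patterns checked. One-sided error = 1 − Φ(1.96 × ratio).

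| Visit SDs | Root mean square | Month-12 ratio | Month-12 one-sided error | Month-3 ratio | Month-3 two-sided error |
|---|---|---|---|---|---|
| 7.35 at all four | 7.35 | 1.00 | 2.5% | 1.00 | 5.0% |
| 6, 7, 7.5, 8 | √(205.25/4) = 7.16 | 7.16/8 = 0.895 | 4.0% | 7.16/7 = 1.02 | 4.5% |
| 5.5, 7, 8, 9 | √(224.25/4) = 7.49 | 7.49/9 = 0.832 | 5.1% | 7.49/7 = 1.07 | 3.6% |
| 9, 8, 7.35, 7.35 | √(253.045/4) = 7.95 | 7.95/7.35 = 1.08 | 1.7% | 7.95/8 = 0.99 | 5.1% |

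A pattern with only the first visit lower (5, then 7.35 throughout) gives two-sided errors of 6.8% to 7.5% at both month 3 and month 12.

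**Step 3: the earlier fallback steps.**
- ML instead of REML: SE ratio about √(167/170) = 0.991, so the two-sided error is about 5.2%.
- ARH(1) and CSH: SE ratio 0.97 to 1.03 with complete data.

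**Step 4: simulation with dropout.** The plan's model was fitted by REML with 113:57 subjects, about 12% dropout missing at random, and 1,500 replicates (Monte Carlo error about 0.6 percentage point at 5%).
- Constant SD 7.35, AR(1) or CS: two-sided error 4.9% to 5.7%.
- ARH(1) and CSH, constant or rising SDs: two-sided error 4.5% to 5.7%. The upper tail that decides month 12 was 1.8% to 3.9%; the 3.9% came with a bias of about 0.17 point under ARH(1), while the SE was about right (ratio 0.98).
- SDs 6, 7.35, 8, 9, AR(1) or CS, model-based SE: month-12 two-sided error 10.6% to 11.5%, upper tail 6.3% to 8.1%; month-3 error 3.4% to 4.6%.
- The same case with sandwich SE: month-12 two-sided error 4.9% to 6.1%, upper tail 2.7% to 4.4%; month-3 error 4.9% to 5.3%. The remaining excess goes with a month-12 bias of about 0.08 to 0.22 point.

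**The case against.** **The path is long.** Unstructured must fail under REML and under ML, then ARH(1) and CSH must fail, and then visit variances must differ. With four visits the unstructured matrix has 10 parameters for about 170 subjects. This stands: the event is unlikely, and its probability cannot be computed from the documents.

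**The inflation comes from assumed SDs.** The plan assumes 7.35 at both month 3 and month 12. This stands as far as it goes. The plan gives no SD for the other visits, and one low early visit is enough to shift the pooled variance.

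**Model-based errors are not stated.** True. They are inferred from naming SAS MIXED with no option, and the promised detailed SAP could settle it. The gap is in the current text.

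**The decision would rarely change under the planned effect.** With a true mean of 4.0, n = 100 and SD 9, the correct lower limit averages 4 − 1.984 × 0.9 = 2.2. With the SE multiplied by 0.832 it averages 2.5. Both clear 1. This stands: the error rates above apply when the true mean is 1 point, and trial success also needs the month-3 primary.

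**A stronger reading is not supported.** A reader might infer that the cascade gives wrong error bars for both primaries and all secondaries. It does not do so in general. In the rising-SD cases month 3 is conservative. The secondaries are month-3 contrasts, and no SDs are given for IIEF, SHIM, Qmax or PVR. Nor is the ML step or the visit-order correlation of the heterogeneous structures a material problem for the standard errors.

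**Conclusion.** The concern holds conditionally and is minor. If the cascade reaches AR(1) or CS with default standard errors, and the month-12 SD is above the average over visits, the limit that decides the second primary is too narrow. Its one-sided error is about 4.0% to 5.1% in the two complete-data scenarios with rising SDs, and 6.3% to 8.1% in the simulated case with SDs up to 9 and dropout, against 2.5%. With falling SDs it is about 1.7%. With 7.35 at every visit it is close to nominal. These sizes rest on the assumed visit number, SDs, correlations and dropout.

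It would be wrong to conclude that the primary analysis is invalid or that the error rate is generally inflated. If the unstructured model converges, the point does not arise.

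**What to change.** In the Synopsis and in SAP I.G.a and I.G.c, or in the detailed SAP before unblinding:

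1. On non-convergence, keep REML and the unstructured matrix, and first try other starting values or Fisher scoring.
2. Keep the ordered list of simpler structures as the final safety net, fitted by REML. Removing AR(1) and CS is not needed to repair the standard errors, and would leave no last step if ARH(1) and CSH also failed.
3. State that whenever a structure other than unstructured is used, all tests and confidence intervals, including the month-12 lower limit, use empirical (sandwich) standard errors, and name the degrees-of-freedom method.

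The cost is a few lines of text and one option in the model call; the main analysis is unchanged if unstructured converges. The downside is a slightly noisier standard error in the rare case that the fallback is used, small at about 170 subjects. Sandwich errors do not remove bias from a wrong correlation structure when data are missing at random, so the report should state which structure was used and why.
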